This trial will be registered on Clinical Trials.gov. It is the intent that these data may be used for to support regulatory clearance and/or consideration for a submission to peer review publication.

XVI. Risk and Benefit Analysis

A. Potential Risks and Discomforts

This is a minimal risk study. Potential risks are detailed below and will be listed in the ICF and discussed during the consenting process.

We believe that the risks of providing noninvasive ventilation with the Vector NIV device are no greater than the risks encountered with other assisted positive airway pressure (PAP) devices. We believe that no significant risks will be posed to the participants participating in this protocol, as the study is noninvasive and will be conducted in a clinical

Determination of the Prevalence and Severity of Expiratory Flow Limitation in Chronic Obstructive Pulmonary Disease Patients

supervised setting by trained clinical staff. The equipment has been tested to ensure safety. Should the equipment not perform as designed, therapy could increase and / or decrease more than desired. This affect could be uncomfortable.

A trained study staff member will be present monitoring the participant while the device is in use at the clinic. The study staff member will intervene should any problems be identified. One possible intervention could be for the staff to stop the study in the event that participant's oxygen saturation (SpO_2) falls below 88%. The participant can also easily remove their interface device should it become uncomfortable or make breathing difficult. Other potential side effects of PAP therapy may include: ear discomfort, conjunctivitis, skin abrasions due to non-invasive interfaces and gastric distension (aerophagia), all of which are quite uncommon. Thus, we believe that the risks and discomfort are minimal.

COVID-19 is a risk with any in-person activity, but proper mitigation strategies, including COVID-19 screening, disinfection, and other site safety procedures, will be implemented to minimize patient risk.

We believe that the risks and discomforts associated with this study are minimal.

B. Potential Benefits

Although participation in this trial will not result in any direct benefit to the subjects, they will be contributing to generalizable data that will help provide the sponsor and investigator more insight into the prevalence of expiratory flow limitation in the COPD patient population.

C. Compensation for Research-Related Activities

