3.0	Clarification of SAE reporting language, addition of [name] as study monitor and contact for AE reporting, addition of COVID-19 risk and precautions, update to Philips name/address/logo, administrative changes	09/MAR/2021	[name], [name]
4.0	Clarification of EFL definition, updates to objectives and endpoints, administrative changes	12/APR/2022	[name], [name]

Glossary

Apnea: the cessation of airflow at the nostrils and mouth for at least 10 seconds.

Apnea/Hypopnea Index (AHI): the number of apneas and hypopneas per hour of sleep.

AVAPS: Automatically adjusts pressure to meet a target tidal volume. Inspiratory pressure fluctuates between the minimum and maximum settings to reach the set Tidal volume

Bi-Level PAP Therapy: Two levels of pressure therapy, one during inspiration IPAP and another during expiration EPAP.

COPD: Chronic Obstructive Pulmonary Disease

CPAP Therapy: Continuous Positive Airway Pressure – delivers a constant pressure during inspiration and expiration.

ODI: 4% Oxygen Desaturation Index

EFL: Expiratory Flow Limitation - occurs when the airways become compressed which usually results when a pressure outside the airway exceeds the pressure inside the airway

EPAP: Expiratory Positive Airway Pressure-Physician prescribed pressure for the expiratory (breathing out) phase of an individual on Bi-level PAP therapy

FEV₁: Forced Expiratory Volume in one second – the volume of air exhaled in the first second of the FVC maneuver and is the most reproducible measurement of airway obstruction.

Final EPAP: EPAP that is determined to abolish EFL.

FOT: Forced Oscillation Technique – A method to detect the presence of expiratory flow limitation.

FVC: Forced Vital Capacity – Spirometry measurement in which the patient inhales maximally and then exhales as rapidly and completely as possible.

IPAP: Inspiratory Positive Airway Pressure - Physician prescribed pressure for the inspiratory (breathing in) phase of an individual on Bi-level PAP therapy.

Noninvasive Positive Pressure Ventilation (NPPV): mechanical ventilation provided noninvasively (by mask or similar interface) rather than through an endotracheal tube or tracheostomy.

Determination of the Prevalence and Severity of Expiratory Flow Limitation in Chronic Obstructive Pulmonary Disease Patients

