- between 2.8 and 3.8 cm H₂O/l/s, inclusive, have indeterminate EFL. Some breaths were calculated to be flow limited.
- greater than 3.8 cm H₂O/l/s have EFL.

For purposes of this trial, participants who have indeterminate EFL or EFL (i.e., $\Delta\bar{X}_{rs}$ value is greater than or equal to 2.8 cm H₂O/l/s) will continue to titration.

This technology has been evaluated in numerous clinical studies for both the detection, reduction and abolishment of expiratory flow limitation in patients with COPD. In 1956, Dubios et al., demonstrated the FOT method to be applicable to the measurement of airway resistance in patients, evaluation of therapeutic procedures designed to relieve airway obstruction, separation of airway resistance from tissue resistance, and study of the multiple factors that may affect airway resistance.¹ And in additional work 2006, Dellaca et al., suggested the forced oscillation technique may be useful in chronic obstructive pulmonary disease patients using nasal pressure support by identifying continuous positive

Determination of the Prevalence and Severity of Expiratory Flow Limitation in Chronic Obstructive Pulmonary Disease Patients

airway pressure levels that support breathing without increasing lung volume, which in turn increase the work of breathing and reduce muscle effectiveness and efficiency.⁶

The Vector project has incorporated this method as a new feature into the Philips BiPAP Ventilator (Murrysville, PA) overall platform (K121623). The device has been designed to produce a 5 Hz sine wave with peak-to-peak amplitude of approximately 2 cmH₂O superimposed upon the pressure and flow generated by the device. The resultant feedback waveform is then filtered and analyzed to measure reactance (delta X_{rs}) and thus determine if EFL is present. Subsequently, the EPAP (and concurrently and proportionally the IPAP) is increased until the EFL is essentially abolished (falls below the predetermined EFL threshold). Since this reactance is analyzed continuously (breath by breath) during both inspiration and expiration, it is relatively immune to external factors such as modest leaks or coughing / swallowing.

Description of the Intervention Studied

Study Device Descriptions:

1. Vector Device

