The Resmon Pro (St. Paul, MN) also uses the forced oscillation technique (FOT) which is a noninvasive method to measure the mechanical properties of the lung and airways during tidal breathing. In addition to measuring total impedance (resistance and reactance), the Resmon Pro can measure expiratory flow limitation which is a key index of respiratory obstruction. Restech has developed patented technology to determine the breath-by-breath presence and severity of expiratory flow limitation (EFL) during quiet breathing. Using the Resmon Pro, a physician can detect the presence, severity and reversibility of EFL, and evaluate the degree of airflow obstruction and shortness-of-breath experienced by the patient.

The Resmon PRO FULL (K152585) is intended to measure respiratory system impedance using the Forced Oscillation Technique (FOT). Is intended for use with pediatric and adult patients 4 years of age or older. The device is designed to be used by pulmonologists, general practitioners, nurses, respiratory therapists, laboratory technologists, medical researchers and similarly trained personnel in hospitals, clinics, and private physician offices.

Resmon PRO FULL consists of a main unit which has been designed to be used stand-alone, without the need of any personal computer, and an adjustable holder with a clamp to fix such unit to a table/desk and to regulate its height and orientation to the patient during an FOT test.

II. Study Objectives and Purpose

Primary Objective

To gain insight and understanding on the prevalence and severity of expiratory flow limitation and how it relates to other physiological characteristics and endpoints in patients with COPD. For purposes of this trial, overall prevalence includes indeterminate EFL and EFL.

Secondary Objectives: To understand the correlation of the final EPAP with FEV1, final EPAP with screening delta Xrs value and the percent of participants with EFL per the Resmon Pro that have their EFL abolished during the Vector screening.

Primary Endpoint:

- Overall Prevalence of EFL, as defined as the percentage of participants exhibiting a Delta Xrs value greater than or equal to 2.8

Secondary Endpoint:

- Correlation of titrated Final EPAP to participants' FEV1
- Correlation of titrated Final EPAP to participants' screening Delta Xrs value
- Percent of participants with EFL per the Resmon Pro that have their EFL abolished during the Vector screening

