- EFL Determination: The participant will be asked to breathe quietly into the Vector device using the selected mask for 5 minutes in the seated position, and then an additional 5 minutes while in the supine or semi-recumbent position. This device has the capability of detecting EFL. If it is determined that the participant does not have EFL or indeterminate EFL by the device screening indicator, the participant will not continue with the EPAP titration.
- EPAP Titration: if it is determined by the Vector NIV device that the participant has indeterminate EFL or EFL (ΔX_{rs} value is greater than or equal to 2.8 cm H₂O/l/s)

Determination of the Prevalence and Severity of Expiratory Flow Limitation in Chronic Obstructive Pulmonary Disease Patients

the Vector NIV device will be changed from screening mode to therapy mode to delivery BiPAP therapy with the following settings.

Vector Device Settings:

• Pressure Support	6 cmH ₂ O
• Max Pressure	26 cmH ₂ O
• EPAP Min / EPAP Max	4 / 20 cmH ₂ O

- The participants will then breathe on the Vector NIV device in the supine position (preferred) or semi-recumbent if needed for approximately an additional 20 minutes. During the additional 20 minutes of breathing, the device will automatically increase the EPAP (and concurrently and proportionally the IPAP) until the EFL is abolished (or falls below the predetermined EFL threshold).
- While the automatic EPAP Titration is being performed, all participants' SpO₂ will be monitored via finger pulse oximetry.
- Patient must stay awake during the EPAP Titration. If the patient falls asleep, they will be woken by study staff.
- The Final EPAP that is determined to abolish the participants' EFL will be recorded. This value may be assessed by a Philips staff member using a software program designed to determine this value.
- Participants will complete an EFL Vector device post questionnaire

Unscheduled Visits:

This is a single visit study. There are no anticipated unscheduled visits.

IV. Selection and Withdrawal of Subjects:***A. Inclusion Criteria***

1. Age \geq 40 years of age; \leq 80 years of age
2. Ability to provide consent
3. Diagnosis of COPD

B. Exclusion Criteria:

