1. Any major non COPD uncontrolled disease or condition, such as congestive heart failure, malignancy, liver or renal insufficiency (that requires current evaluation for liver or renal transplantation or dialysis), amyotrophic lateral sclerosis, or severe stroke, or other condition as deemed appropriate by investigator as determined by review of medical history and / or participant reported medical history

Determination of the Prevalence and Severity of Expiratory Flow Limitation in Chronic Obstructive Pulmonary Disease Patients

2. Suffering from a COPD exacerbation at the time of data collection or in the 30 days prior to data collection
3. Self-reported Pregnancy
4. Employee or family member that is affiliated with Philips Respironics
5. History of bullous emphysema
6. History of pneumothorax
7. Evidence of acute sinusitis or otitis media
8. Hypotension
9. Participants at risk for aspiration of gastric contents
10. Epistaxis
11. Participants in respiratory failure
12. Inability to maintain a patent airway or adequately clear secretions

C. Withdrawal:

The term “discontinuation” refers to the participant’s premature withdrawal from the study prior to completing all procedures. Participants may be discontinued from the study for any of the following reasons:

- If in the investigator’s judgement, continuation in the study may prove harmful to the participant. Such a decision may be precipitated by adverse events, including fever, nausea, rash, changes in vital signs, or the development of a new medical condition. The investigator will be solely responsible for making medical/safety decisions regarding the participant’s continued participation in the study.
- Noncompliance;
- At the request of the participant.

The study team will document whether or not each participant completed the study. If, for any participant, study treatment or assessments were discontinued, the reason will be recorded.

The study goal is to have 100 participants successfully complete the study.

V. Treatment of Subjects:

A. Intended Use

Vector Device Intended Use

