- Ventilator collected parameters during the EFL screening and titration; delta Xrs value, % flow limited breaths, EPAP values and mask leak values.

VII. Assessment of Safety

All serious adverse events occurring during the course of the study and up to 72 hours post study visit will be collected, fully documented, and reported to Western Institutional

Determination of the Prevalence and Severity of Expiratory Flow Limitation in Chronic Obstructive Pulmonary Disease Patients

Review Board by the Principal Investigator, [name], MD or sponsor staff per IRB guidelines. Serious adverse events will be reviewed by the Sponsor within 24 hours of the study team being aware of the event.

A serious adverse event (SAE) is an adverse event:

- Resulting in death, or
- Resulting in a serious deterioration in the health of the subject that:
 - Results in a life-threatening illness or injury,
 - Results in a permanent impairment of a body structure or body function,
 - Requires inpatient hospitalization or prolongation of existing hospitalization, or
 - Results in medical or surgical intervention to prevent permanent impairment of a body structure or body function.

All unexpected adverse events during the course of the study and up to 72 hours post study visit will be collected and reviewed. As any events will be reported electronically or directly from a person, the study team will collect the onset, duration, intensity and treatment required, outcome and action taken. In addition to adverse event reporting, the study staff will report a summary of the protocol findings, participant recruitment, drop-outs, and events to the IRB annually.

VIII. Device Deficiencies

All device deficiencies, use or user errors, and equipment failures will be documented.

Use or User errors will be captured as part of the source documentation. Device deficiencies and equipment failures will be kept on a separate log. The serial numbers and type of deficiency/failure will be captured. Unanticipated device deficiencies that lead to SAE's will be reviewed with the PI and reported to the IRB as required.

IX. Statistical Methods

Determination of Sample Size

Approximately 100 participants will be enrolled. No power analysis was performed.

General Considerations

Descriptive statistics will be presented for all variables of interest. Continuous data will be summarized by mean, standard deviation, median, minimum, and maximum values.

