Categorical data will be presented as frequencies and percentages. Any formal significance testing will be performed at $p < 0.05$.

There are no statistical criteria for terminating the study, and any deviations to the original statistical plan will be noted in the analysis report.

Determination of the Prevalence and Severity of Expiratory Flow Limitation in Chronic Obstructive Pulmonary Disease Patients

Primary Analysis

The primary analysis will calculate the prevalence of EFL, including the 95% Binomial confidence interval (CI).

Secondary Analysis

Correlations between device parameters and efficacy outcomes will be performed using Pearson and Spearman correlation. Percentage of participants exhibiting EFL abolition with Vector therapy will be presented, including the 95% Binomial confidence interval (CI).

Exploratory Analysis

Various exploratory analyses may be performed to help evaluate participant's therapy settings with other baseline data or outcomes, but these analyses are not required for the final report

Participant Disposition

Participant disposition, including the total number of participants enrolled, completed, early terminations and withdrawals, will be presented. A listing will be provided with the reasons for discontinuation.

Safety Analysis

Safety evaluations will be performed by recording clinical adverse events at the time originally reported, and they will be followed at regular intervals until resolution or study completion, whichever comes first. Adverse events will be provided in data listings.

Interim Analysis

An interim analysis may be performed after approximately 50% of the planned study population has completed the study.

X. Direct Access to Source Data / Documents

Only site clinical study staff will know the identity of the participants. All information recorded by the study team and provided for analysis will be given a study ID number.

Privacy rules and requirements according to federal and state governing regulations will be implemented. All the information collected as part of this study will be kept confidential. All information collected for this study will be kept in a secured area or stored in a password protected computer if digital. Except when required by law, participants will not be identified by name, social security number, address, telephone number, or any other direct personal identifier in study records. For records disclosed to Philips participants will be assigned a unique code number.

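### The Final EPAP versus screening Delta Xrs correlation is computed in a sample cut off on Delta Xrs itself, so its size depends on the cut-off and the distribution; a regression slope with 95% CI should be the main estimate

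*Combined protocol and SAP*

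**What the plan says.** Section II lists three secondary endpoints. Two are correlations of titrated Final EPAP, one with FEV1 and one with the screening Delta Xrs value: "To understand the correlation of the final EPAP with FEV1, final EPAP with screening delta Xrs value".

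The Glossary defines Final EPAP as the "EPAP that is determined to abolish EFL". Section I says that a participant whose Delta Xrs "value is greater than or equal to 2.8 cm H₂O/l/s) will continue to titration". Section III (EFL Determination) says that if Vector screening shows neither EFL nor indeterminate EFL, "the participant will not continue with the EPAP titration".

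Section IX (Secondary Analysis) says that the correlations "will be performed using Pearson and Spearman correlation". It names no analysis set, expected number, confidence interval or slope for them. On sample size it says: "Approximately 100 participants will be enrolled. No power analysis was performed". Section IV.C adds: "The study goal is to have 100 participants successfully complete the study".

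**The concern.** The variable that decides who gets a Final EPAP is also one of the two variables being correlated. A correlation coefficient depends on the spread of the sample as well as on how much EPAP changes per unit of Delta Xrs. Removing everyone below 2.8 changes that spread, so r can change although the underlying relation does not. FEV1 is not the selection variable, but it is likely to track Delta Xrs, so the selection reaches that correlation too.

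Two of the three secondary endpoints are involved. Section II frames the aims in terms of patients with COPD and Section III describes a community COPD population, so a coefficient from the titrated subset could be read as applying to all of them. The same physiology could also give a different r in another study with a different severity mix or cut-off. The primary prevalence endpoint is not affected.

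**Working it through.** The plan has no power or precision figure for these correlations to reproduce; the only planning number is about 100 participants.

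**Inputs from the documents.** N about 100 (Section IX); titration only at Delta Xrs ≥ 2.8 (Sections I and III); EPAP limits 4 and 20 cmH2O (Section III).

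**Assumptions, because the documents give no values.** Prevalence p of Delta Xrs ≥ 2.8 of 30, 40 or 50%. Full-range correlations: Delta Xrs with EPAP need 0.70, Delta Xrs with FEV1 −0.50, EPAP need with FEV1 −0.50. Normality in steps 1 to 3.

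**Step 1: loss of spread.** For a standard normal variable kept above c = Φ⁻¹(1 − p), let λ = φ(c)/p. The retained variance is v = 1 + cλ − λ², and the SD ratio is u = √v.

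| p | n of 100 | c | λ | v | u |
|---|---|---|---|---|---|
| 30% | 30 | 0.524 | 1.159 | 0.264 | 0.514 |
| 40% | 40 | 0.253 | 0.966 | 0.312 | 0.558 |
| 50% | 50 | 0 | 0.798 | 0.363 | 0.603 |

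**Step 2: Final EPAP with Delta Xrs (direct selection).** r′ = r·u / √(1 − r² + r²u²), with r = 0.70.

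- 30%: 0.70 × 0.514 / √(0.51 + 0.49 × 0.264) = 0.45
- 40%: 0.70 × 0.558 / √(0.51 + 0.49 × 0.312) = 0.48
- 50%: 0.70 × 0.603 / √(0.51 + 0.49 × 0.363) = 0.51

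In simulation the regression slope stayed at about 0.70 (SD units) throughout.

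**Step 3: Final EPAP with FEV1 (indirect selection).** With k = v − 1, r′ = (−0.50 + 0.70 × (−0.50) × k) / √[(1 + 0.49k)(1 + 0.25k)].

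- 30%: −0.243 / √(0.640 × 0.816) = −0.34
- 40%: −0.259 / √(0.663 × 0.828) = −0.35
- 50%: −0.277 / √(0.688 × 0.841) = −0.36

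**Step 4: does r always fall?** Normality was replaced by a lognormal Delta Xrs with a linear relation (2,000,000 draws, 30% prevalence). The slope is in full-range SD units.

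| Log-SD of Delta Xrs | r, from 0.50 | slope | r, from 0.70 | slope |
|---|---|---|---|---|
| 0.25 | 0.38 | 0.50 | 0.58 | 0.70 |
| 0.50 | 0.48 | 0.50 | 0.68 | 0.70 |
| 0.75 | 0.56 | 0.50 | 0.75 | 0.70 |
| 1.00 | 0.62 | 0.50 | 0.80 | 0.70 |

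The coefficient falls, holds or rises with the skew. The slope does not move.

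**Step 5: precision.** By Fisher's z, with half-width 1.96/√(n − 3), an observed r of 0.50 has a 95% CI of 0.17 to 0.73 at n = 30 and 0.26 to 0.68 at n = 50, against 0.34 to 0.63 at n = 100.

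**Step 6: could untitrated participants be brought back in?** One candidate is a rank analysis of everyone screened, with Vector-negative participants tied at the lowest EPAP. It was tested with Final EPAP set to pure noise among titrated participants and Delta Xrs–FEV1 at −0.50 (2,000 trials of 100 at each of 30, 40 and 50%). Spearman with Delta Xrs still averaged 0.77 to 0.81 and was significant in every trial. With FEV1 it averaged about −0.37 and was significant in 97 to 98%. That analysis returns the selection rule, not information about Final EPAP.

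**The case against.** The strongest reply is that the population is built into the endpoint. Someone without EFL has no pressure that abolishes it, so the correlation among titrated participants is the endpoint as written, not a biased estimate of a full-range correlation that the protocol never claims. This largely stands: the subset correlation is a legitimate target. What remains is that Section IX does not say the result applies only to that subset, and that r is a poor summary there because it depends on where the cut falls.

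A second reply is that the aims are descriptive, no power is claimed, and both Pearson and Spearman are already planned. That limits the stakes. Spearman does not solve the problem, because it is computed in the same truncated sample.

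A reader might infer that both correlations will be understated. The documents do not support that. They give no distribution, prevalence or correlation, and step 4 shows that r may hold or rise under right skew.

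A reader might also infer that data from untitrated participants are being wasted and should be ranked lowest. No section assigns an EPAP to those participants, and step 6 shows that doing so creates a strong correlation by construction.

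**Conclusion.** The point holds in a limited form. It follows from the Glossary and Sections I to III that Final EPAP is available only at Delta Xrs ≥ 2.8, and Section IX offers only coefficients whose size depends on that cut-off and on the Delta Xrs distribution. Under the assumed normal model, 0.70 becomes 0.45 to 0.51 for Delta Xrs, and −0.50 becomes −0.34 to −0.36 for FEV1, at 30 to 50% prevalence. These figures illustrate the possible size; they do not predict this study's result, and the direction is uncertain.

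The slope on Delta Xrs is robust to this selection if the relation is linear and the Delta Xrs used is the reading that decided titration. The FEV1 endpoint has no equivalent remedy, because selection is not on FEV1; it can only be labelled correctly. This is an inexpensive improvement to two secondary endpoints and does not threaten the primary result.

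**What to change.** In Section IX, Secondary Analysis:

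1. For Final EPAP versus screening Delta Xrs, report the linear regression slope (cmH2O per cmH2O/l/s) with 95% CI beside the planned coefficients, and name it as the main estimate. State which screening reading is used, since Section III takes one seated and one supine or semi-recumbent; it should be the Vector reading that decides titration.
2. Check linearity with a scatter plot and residuals. Look for values piling up at the 4 and 20 cmH2O EPAP limits, and report how many titrated participants have no Final EPAP because EFL was not abolished. Either can bias the slope.
3. Report both correlations with n and 95% CI, labelled as applying to titrated participants (Delta Xrs ≥ 2.8) and not to all COPD patients.
4. Do not add an all-screened analysis that ranks Vector-negative participants lowest.

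The cost is a few sentences in Section IX and one regression, using data already collected. The slope relies on linearity, which a small titrated group can check only roughly.
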